7.3. Events or Outcomes Qualifying as AEs or SAEs

7.3.1. Clinical laboratory parameters

Abnormal laboratory findings (e.g., clinical chemistry, hematology) or other abnormal assessments (e.g. vital signs) that are judged by the investigator as **clinically significant** will be recorded as AEs or SAEs if they meet the definitions of sections 7.1 and 7.2 respectively. Clinically significant abnormal laboratory findings or other abnormal assessments that are detected during the study or are present at informed consent and significantly worsen during the study will be reported as AEs or SAEs. Clinically significant abnormal laboratory findings or other abnormal assessments that are associated with the disease being studied and are present at the start of the study but do not worsen, will **not** be reported as AEs or SAEs. However, if these findings or assessments are judged by the investigator to be more severe than expected considering the patient's condition, then they may be reported as AEs or SAEs.

7.3.2. Pregnancy report

Patients who become pregnant at any time will be immediately withdrawn from participation in the study. All appropriate withdrawal assessments may be performed at the discretion of the investigator.

The investigator will collect pregnancy information on any woman patient or partner of a male patient, who becomes pregnant and their partner while participating in this study. The investigator will record pregnancy information on a specific pregnancy notification form and submit it to IntuVigilance Limited (see contact details in section 8.4) within 24 hours after knowledge of a patient's or partner's pregnancy. The patient or partner will also be followed to determine the outcome of the pregnancy, be it full-term or prematurely terminated. Information on the status of the mother and child will be forwarded to IntuVigilance Limited. Follow-up will normally end 6 to 8 Weeks following the estimated delivery date.

While pregnancy itself is not considered to be an AE or SAE, any pregnancy complication or elective termination of a pregnancy for medical reasons will be recorded as an SAE. A spontaneous abortion is always considered to be an SAE and will be reported as such.

The time period for collecting pregnancy information is identical to the time period for collecting AEs, as stated in Section 7.4, Time Period, Frequency, and Method of Detecting AEs and SAEs. Pregnancy information is collected from the signing of informed consent to 4 Weeks after the last dose.

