In the minipig, in the 14-day study, ABX464 oral treatment induced a reduced food intake associated with body weight loss for dose levels of 10 mg/kg o.d and above, which resolved after termination of treatment. In the 3-month study, ABX464 at dose levels of 5, 10 and 15 mg/kg o.d. was well tolerated since no findings of toxicological importance were described. However, toxic effects appeared shortly before completion of the third month of treatment in the 26/39 Weeks study in minipigs at the same dose-levels. The main adverse finding was centrilobular hepatocellular degeneration/necrosis associated with hemorrhage, fibrosis and /or extramedullary hematopoiesis observed at dose levels of 10 mg/kg and above. The liver lesions observed in the single animal administered 5 mg/kg o.d. were not considered adverse. Based on this observation, the NOAEL was considered to be 5 mg/kg o.d.

ABX464 was found to be non-genotoxic. Its main metabolite, the ABX464-N-Glu was not mutagenic as assessed by an Ames test, an in vitro and an in vivo micronucleus assay.

Reprotoxicity assessed from fertility to postnatal development, was explored in five studies. In rabbits, the maternal NOAEL was considered to be 9 mg/kg o.d. and the NOAEL for the embryo-fetal development less than 1 mg/kg o.d. In rats, the maternal NOAEL and the NOAEL for pup development and survival is considered to be lower than 15 mg/kg o.d.. The F1 generation NOAEL is considered to be 40 mg/kg o.d. in absence of adverse effect at this dose-level.

It is likely that ABX464 has teratogenic activity and the main target organs of ABX464 toxicity were found to be the gastro-intestinal tract and the liver.

No signs of hepatotoxicity have been observed in any of the patients treated with ABX464 in the previously conducted or on-going clinical trials. ABIVAX and its clinical experts consider that patients treated with ABX464 are not at increased risk of developing a drug-induced hepatotoxicity.

A specific liver function monitoring plan has been implemented in the current clinical study.

Regarding the other observations made from the pre-clinical toxicology program, please refer to the current version of the Investigator Brochure.

1.2.6.Previous clinical experience with ABX464

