- Females and males receiving the study treatment and their partners must agree to use a highly effective contraceptive method during the study and for 6 months after end of study or early termination. Contraception should be in place at least 2 weeks prior to screening. Women must be surgically sterile or if of childbearing potential must use a highly effective contraceptive method. Women of childbearing potential (WOCBP) will enter the study after confirmed menstrual period and a negative pregnancy test. Highly effective methods of contraception include true abstinence, intrauterine device (IUD) or hormonal contraception aiming at inhibition of ovulation, intrauterine hormone releasing system, bilateral tubal ligation, vasectomized partner. True abstinence is defined when this is in line with the preferred and usual lifestyle of the patient. In each case of delayed menstrual period (over one month between menstruations)

confirmation of absence of pregnancy is required. This recommendation also applies to WOCBP with infrequent or irregular menstrual cycle. Female and male patients must not be planning pregnancy and male patients should use condom and must not donate sperm during the trial and for 6 months post completion of their participation in the trial.

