7.4. Time Period, and Frequency of Detecting AEs and SAEs

All AEs and SAEs occurring from the time a patient consents to participate in the study until 4 Weeks after he or she has completed or discontinued the investigational product must be recorded in the Patient's eCRF.

Moreover, any occurrence of pregnancy within 6 months post stopping dosing must be reported.

Importantly, SAEs will have to be reported, either by email or by Fax, to IntuVigilance Limited within 24 hours of awareness of an SAE.

IntuVigilance Limited

[name]

Hotline [contact]

Email Address: [contact]

[contact]

Legislative guidance requires the investigator to also ensure that any **related** SAEs are reported after the patient finished the study if the investigator becomes aware of them.

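### Protocol 7.3.2 ends pregnancy collection 4 weeks after the last dose, 7.4 requires reporting for 6 months, and only 7.3.2 says how to notify and follow up

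*Protocol*

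**What the plan says.** Protocol 7.3.2 is the protocol's only section on handling pregnancies. It fixes the period in two sentences. The first ties it to the adverse event period: "The time period for collecting pregnancy information is identical to the time period for collecting AEs, as stated in Section 7.4". The second spells that period out: "Pregnancy information is collected from the signing of informed consent to 4 Weeks after the last dose". The same section limits its subject to a female patient, or the partner of a male patient, "who becomes pregnant and their partner while participating in this study". It also contains the whole procedure:

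- a dedicated notification form, sent to the safety vendor within 24 hours of knowledge;
- follow-up to the outcome, normally ending 6 to 8 weeks after the estimated delivery date;
- rules on which pregnancy outcomes count as serious adverse events.

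Protocol 7.4 sets the period for adverse events and serious adverse events as running "until 4 Weeks after he or she has completed or discontinued the investigational product". It then adds a separate sentence on pregnancy: "Moreover, any occurrence of pregnancy within 6 months post stopping dosing must be reported". That sentence names no form, deadline or outcome follow-up.

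Two other places give context. Protocol 1.2.5.1 concludes from the reproductive toxicity studies: "It is likely that ABX464 has teratogenic activity". Protocol 4.2.1 requires contraception during the study and "for 6 months after end of study or early termination".

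**The concern.** Section 7.3.2 misdescribes the section it cites. It calls the pregnancy period identical to the adverse event period in 7.4, yet 7.4 gives pregnancy a longer period of its own. A site that treats the dedicated pregnancy section as the full instruction has a stated reason to stop at 4 weeks.

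At stake is the capture and outcome follow-up of pregnancies beginning after that point, for a drug the protocol itself regards as probably teratogenic. Such events will be few in a trial of up to 60 patients, but each one matters individually.

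**Working it through.** The documents give no figure to reproduce. The check sets the two sections side by side and then does calendar arithmetic.

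| Item | Protocol 7.3.2 | Protocol 7.4 |
|---|---|---|
| End of pregnancy window | 4 weeks after last dose | 6 months after stopping dosing |
| Notification form | Yes | Not mentioned for pregnancy |
| 24-hour submission | Yes, for pregnancy | Stated for serious adverse events only |
| Outcome follow-up | To 6 to 8 weeks after estimated delivery | Not mentioned |

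**Size of the discrepancy**

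1. The 7.3.2 window is 4 × 7 = 28 days after the last dose.
2. The 7.4 window is 6 × 30.44 ≈ 183 days after the last dose, taking a month as 30.44 days.
3. The difference is 183 − 28 = 155 days, and 155 / 7 ≈ 22 weeks. As a share of the longer window it is 155 / 183 ≈ 85%.

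**Placed on the trial calendar for a patient who completes treatment**

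1. The last dose is on Day 83 (Protocol 5.6.1 and 6.1).
2. The 7.3.2 limit falls on Day 83 + 28 = Day 111.
3. The 7.4 limit falls near Day 83 + 183 = Day 266.
4. The last scheduled pregnancy test is at the End of Study visit, Day 105 ± 2 (Protocol 5.2.5 and 5.3.3). It precedes both limits, so this protocol schedules no contact in the interval where the two sections disagree.

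**What applies to a pregnancy in that interval**

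Under 7.4 it must be reported. Under 7.3.2 it lies outside the collection period, so the form, the 24-hour clock and the outcome follow-up have no stated application to it. The rules on serious events leave a related doubt. Section 7.3.2 always classes a spontaneous abortion as serious. Section 7.4 ends routine recording of serious events at 4 weeks, and after the patient has finished the study it asks only for related ones that come to the investigator's attention.

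Outdated cross-references make the right instruction harder to find. Section 5.3.3 sends a positive test to section 8.3.2, and 7.3.2 sends the reader to section 8.4 for contact details. In the body of the protocol, 8.3 is Pharmacokinetics and 8.4 is Safety Analyses.

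**The case against.** The strongest reply is that the longer duty already exists and is mandatory. Section 7.3.2 itself points to 7.4 for the period, and the 6-month sentence there directly follows the adverse event window. A reader might infer that pregnancies in months 2 to 6 are covered by no rule, or that sites would stop asking at 4 weeks. The documents support neither. The 22 weeks measure a disagreement between two statements, and a site might, not would, stop at the shorter one.

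The two sections can also be read together: 7.3.2 governs pregnancies arising during participation, and 7.4 adds notice of later ones. That reading is possible, but the protocol does not state it. It leaves the claim of identical periods wrong, and it leaves later pregnancies with no stated form or outcome follow-up. Protocol 7.1 lets the post-treatment reporting period be extended if the drug is strongly suspected not to have been eliminated. That provision is discretionary, gives no length, and does not settle the matter.

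Four further limits stand:

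- **Rollover.** Patients entering ABX464-302 start that study's drug on Day 84 under a separate protocol. The documents do not give the proportion who will.
- **Primary objective.** A reader might infer that the primary safety result is at risk. The primary endpoint is the incidence of treatment-emergent adverse events. Section 7.3.2 says pregnancy itself is not an adverse event, SAP 11.6.1 counts treatment-emergent events only up to study closure or withdrawal, and SAP 11.6.2 only lists serum pregnancy data.
- **Contraception.** The 6 months in Protocol 4.2.1 run from end of study or early termination. That is a rule on contraception, not a collection window, so it contradicts neither section.
- **Exposure.** The documents give no elimination half-life or washout time for ABX464. They do not show that a pregnancy conceived months after the last dose would be exposed.

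**Conclusion.** The point holds as an internal contradiction in safety reporting. Sections 7.3.2 and 7.4 give pregnancy windows that differ by about 155 days (22 weeks), taking 6 months as 183 days, and 7.3.2 wrongly calls its period identical to that in 7.4. Because the notification and follow-up procedure appears only under the shorter window, a site relying on 7.3.2 might not collect, or might not follow to outcome, a pregnancy that 7.4 requires it to report. The patients mainly affected are those who leave after this study; their number is unknown.

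The conclusion rests on the text of the two sections and needs no assumption about how often pregnancies occur or whether they are exposed. It does not extend to the primary safety comparison, efficacy or power. It should be corrected, given what the protocol says about teratogenicity and how little the correction costs.

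**What to change.** The sponsor should reconcile Protocol 7.3.2 and 7.4 to a single pregnancy collection window with one start, one end and one reference point, worded identically in both. Which window applies is for the sponsor to decide.

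Section 7.3.2 should then say that its notification form, 24-hour submission, outcome follow-up and classification of serious outcomes apply throughout that window. Its limitation to pregnancies arising during participation should be brought into line. The outdated cross-references in 5.3.3 and 7.3.2 can be corrected in the same edit.

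The cost is wording in adjacent subsections of the protocol. No SAP analysis, sample size or visit schedule has to change. How sites would learn of pregnancies after the last visit is a separate question: the contradiction does not require an answer to it, and any added contact would carry its own cost.

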7.4. Time Period, and Frequency of Detecting AEs and SAEs

All AEs and SAEs occurring from the time a patient consents to participate in the study until 4 Weeks after he or she has completed or discontinued the investigational product must be recorded in the Patient's eCRF.

Moreover, any occurrence of pregnancy within 6 months post stopping dosing must be reported.

Importantly, SAEs will have to be reported, either by email or by Fax, to IntuVigilance Limited within 24 hours of awareness of an SAE.

IntuVigilance Limited

[name]

Hotline [contact]

Email Address: [contact]

[contact]

Legislative guidance requires the investigator to also ensure that any **related** SAEs are reported after the patient finished the study if the investigator becomes aware of them.

7.5. Recording AEs and SAEs

Severity of AEs will be assessed according to CTC-AE Classification Version 5.0.

Patients will be asked to report all AEs as part of the procedures performed at each study visit. The site personnel will document all AEs in the patient's medical record. All AEs subsequently must be recorded in the appropriate eCRF sections.

The following points must be recorded for each event:

- A description of the event in medical terms, not as reported by the patient;
- Date of onset (start date);
- Date of resolution (stop date);
- The time of onset with respect to administering the investigational product;
- The severity of the sign/symptom or clinically significant abnormal laboratory value according to CTC-AE Classification Version 5.0;
- The causal relationship between the investigational product and the occurrence of each AE. This will be assessed by each investigator using clinical judgment. Alternative causes, such as natural history of the underlying diseases, concomitant medications, other risk factors and the temporal relationship of the event to the investigational product will have to be considered. The causality of all AEs should be assessed by the investigator with the following question: Is there a reasonable possibility that the AE may have been caused by the investigational product? And answered "NO" (if not related) and "YES" (if related);
- Action taken regarding the investigational product:
 - No action;
 - Temporary discontinuation;
 - Permanent discontinuation;
 - Patient's outcome:
 - Recovered without sequelae / resolved without sequelae;
 - Recovered with sequelae / resolved with sequelae;
 - Recovering/Resolving;
 - On-going;
 - Fatal (for SAEs only).

If in any one patient, the same AE occurs on several occasions, the AE in question must be documented and assessed a new each time.

7.6. Reporting of SAEs to ABIVAX or its designee

Throughout the study, the reporting of SAEs to the Sponsor or its designee will be done through the SAE forms.

It is the investigator's responsibility to ensure that the SAE report is submitted to IntuVigilance Limited **within 24 hours after knowledge of the event(s)**.

The study specific SAE form should be completed as thoroughly as possible, with all the available details of the event and signed by the investigator or designee. The investigator will assess causality between

the study drug and the adverse event (AE) / serious adverse event (SAE) according to the table outlined below:

Related	A clinical event, including laboratory test abnormality, occurs in a plausible time relationship to treatment administration, and which concurrent disease or other drugs or chemicals cannot explain.
Probably related	A clinical event, including laboratory test abnormality, with a reasonable time sequence to administration of the treatment, unlikely to be attributed to concurrent disease or other drugs or chemicals.
Possibly related	A clinical event, including laboratory test abnormality, with a reasonable time sequence to administration of the treatment, but which could also be explained by concurrent disease or other drugs or chemicals.
Unlikely to be related	A clinical event, including laboratory test abnormality, with a temporal relationship to treatment administration which makes a causal relationship improbable, and in which other drugs, chemicals or underlying disease provide plausible explanations.
Unrelated	A clinical event, including laboratory test abnormality, with little or no temporal relationship with treatment administration. Typically explained by extraneous factors (e.g., concomitant disease, environmental factors or other drugs or chemicals).

An assessment of causality should always be provided at the time of the initial report. If the investigator or designee does not have all information regarding the SAE, he/she should not wait to receive additional information before completing the form and notifying IntuVigilance Limited.

Additional or follow-up information relating to the initial SAE report, will be requested, if necessary. Again, this information is to be completed and submitted through the SAE forms within 24 hours of receipt of the information.

In the rare occasion when the facsimile equipment does not work and in the absence of, the investigator should notify IntuVigilance Limited by telephone within the given timeframe and send a copy of the SAE report form by email.

7.7. Reporting of SAEs to Regulatory Authorities

ABIVAX has a legal responsibility to notify, as appropriate, both the local regulatory authorities and other regulatory agencies about the safety of the investigational medicinal product. It is therefore important that the investigator notifies promptly (within 24 hours) ABIVAX or designee of any SAEs, in order for legal obligations and ethical responsibilities towards other patients to be met.

In addition, the investigator or designee, will comply with the local regulatory requirements (when applicable) in reporting of SAEs to the ethics committee and, if required, to the relevant government authority.

Safety reports on adverse events that are serious AND unexpected AND causally associated with the investigational product are prepared according to ABIVAX's policy and applicable regulations and are forwarded to the investigators. These reports are filed with the investigator brochure or other appropriate study documentation. It is the Sponsor or its designee and/or investigator's responsibility to notify the IRB or IEC of these reports, if applicable according to local requirements.

8. DATA ANALYSIS AND STATISTICAL CONSIDERATIONS

A summary of the principal features of the statistical analysis of the data will be described here, in the statistical section of the protocol. A more technical and detailed elaboration of the principal features stated in the protocol will be given in the first version of the statistical analysis plan (SAP).

Any amendments to the SAP will be clearly documented and signed prior to the final database lock including justifications and details of their potential impact on the interpretation of the study results.

8.1. Statistical and Analytical Plans

No interim analysis is planned.

The study analysis will be performed following database lock upon the completion of the last patient or upon its early discontinuation whichever occurs first.

8.1.1. Protocol deviations

Protocol deviations will be reviewed and classed as major or minor during the blind-review meeting. Major protocol deviations are defined as deviations liable to bias the evaluation of the main efficacy endpoint. The following deviations will be considered as major (non-exhaustive list):

- Noncompliance with the inclusion or exclusion criteria;
- Noncompliance with the study treatment;
- Intake of prohibited medication;
- Noncompliance with time window.

In case of major protocol deviation, the patient must not be randomized (if deviation occurs at baseline) or be discontinued from the study.

